## 8. NUMBER OF SUBJECTS

- *Indicate the total number of subjects to be accrued locally. If applicable, distinguish between the number of subjects who are expected to be pre-screened, enrolled (consent obtained), randomized and complete the research procedures.*
- *If your study includes different cohorts, include the total number of subjects in each cohort.*
- *If this is multisite study, include total number of subjects across all sites.*

Up to 1000 potential participants may be screened for study eligibility. Up to 65 participants will be randomized until 60 (30 participants in each arm) complete research procedures with any data (Fitbit or survey) post- randomization. Eligible participants will be randomized (1:1) into Arm 1 or Arm 2. In Arm 1 (N=30), participants will receive a personalized intervention comprised of three components delivered in a ABCCBA sequence over a total period of 12 weeks, where A- mindfulness, B-yoga, and C-guided walking. During each 2-weeks block, participants will be prompted to complete 3 x 30-minute intervention sessions weekly. In Arm 2 (N=30), participants will receive a personalized intervention comprised of the same three components delivered in a CBAABC sequence over a total period of 12 weeks. Prompts will be delivered weekly to Arm 2 as well.

[figure not shown]

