## 9. STUDY TIMELINES

- *Describe the duration of an individuals participation in the study*
- *Describe the duration anticipated to enroll all study subjects*
- *The estimated date of study completion*

The study will take place over the course of 16 weeks. Participants will begin the trial with a 2-week run-in period during which their baseline sleep duration and adherence to the Fitbit wear and survey submission will be assessed. Following the 2-week run-in period, participants deemed eligible and achieved at least 80% adherence of Fitbit wear and survey submission will be randomized to one of the two intervention arms. Interventions will be delivered by a virtual link to online videos recorded by an experienced Zeel wellness provider. Participants will be limited to three views of the study-provided intervention content each week. During the intervention participants will be asked to wear their

Fitbit device each *day and night*. They will also complete sleep diaries and have their physiological factors assessed using Fitbit devices each day. Participants' perceived stress will be measured using the ecological momentary assessment (EMA); screening for anxiety and depressive symptoms will be assessed using the patient health questionnaire (PHQ-4), a self-report version of the Primary Care Evaluation of Mental Disorders (PRIME-MD). Both EMA and PHQ-4 will be evaluated pre-intervention, bi-weekly during the intervention, and post-intervention. After 12 weeks of receiving the MBI, participants will enter the two-week follow up period to allow for a personalized report of their observed data to be generated.

Fig1. Trial Design

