This study is funded by the National Institute of Aging (NIA) and a requirement of funding is to collect extensive demographic data during the screening process (prior to consent) on eligible participants, and to report this data to the NIA monthly on an individual level by study ID. The intended aim of this requirement is to ensure that funded projects are enrolling diverse populations and that screening does not systematically exclude members of underrepresented groups. These questions have been separated out from demographic data pertinent to the study aims and participants are informed in both the consent and on the study document that they have the option to decline responding to the questions without jeopardizing their ability to participate in the study.

Once potential participants successfully submit their signed consent form, they will receive an onboarding questionnaire to collect more information, including a home address. A Consenting Coordinator will review this information and send the potential participant a message which will include a confirmation of the start date

of their baseline period, and information about what to expect during onboarding to the study. They will receive an initial study kit including a Fitbit device via mail and will receive a copy of their electronically signed HIPAA authorization and consent form with a URL to view the informed consent video that they watched previously.

All baseline periods will begin on a Monday. The baseline period will take place over the course of 2 weeks. Participants will be instructed to continue treating their sleep quality issues as they normally would and not to participate in yoga, mindfulness exercises or walking bouts.

Each morning, baseline participants will receive a survey asking a few questions about their sleep quality the previous night using a modified version of the Consensus Sleep Diary, as well as factors that may have contributed to any sleep issues

During the baseline period, potential participants will be asked to wear their Fitbit all day and night, even while they are sleeping. Participants will be asked to download the Fitbit app to their smart phone. Baseline participants will be instructed to sync their Fitbit device by opening the Fitbit app on their phone at least every two days and to charge their device at least every four days.

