Ten days into the baseline period, a Consenting Coordinator will review individual adherence to Fitbit wear and survey responses. Adherence to Fitbit wear will be defined as recorded activity of greater than 12 hours a day, and recorded sleeping activity greater than 180 minutes in total. Survey adherence will be defined as submission of a given survey. Baseline participants who do not achieve at least 80% adherence of Fitbit wear and survey submission during the first 10 days of the baseline period will be given until day 14 of the trial to obtain 80% adherence. Those who still do not meet 80% adherence by day 14 will be withdrawn from the study. Those participants who do maintain at least 80% adherence during the baseline period will be randomized to one of two intervention sequences in the pilot study. Participants who are randomized to receive intervention sequences will receive confirmation including their protocol timeline. Enrollment will continue until up to 65 participants have been randomized overall, with the goal of reaching 60 participants who complete research procedures with any post-randomization data: 30 participants randomized to receive ABCCBA and 30 participants randomized to receive CBAABC.

Each intervention sequence is made up of six 2-week periods assigning yoga, mindfulness or guided walking. Participants will be limited to 3 (30 minute) intervention sessions each week. During all intervention weeks (12 weeks total), participants will be asked to continue wearing their Fitbit device each day and night. They will continue to receive EMA surveys bi-weekly with questions about their health such as pain, fatigue, concentration, confidence, mood, and stress at that current moment, as well as a daily morning text asking them to report on their

sleep duration and quality the previous night, using a modified Consensus Sleep Diary. At the end of each intervention period on Sunday evening (every two weeks), participants will also receive the PHQ-4 and Perceived Stress Scale (PSS). A study phone number and email address will be available as part of each survey to contact the study team if a participant is concerned about any side effects they are experiencing. Participants will be instructed to contact 911 or go to the nearest emergency room in the event of a medical emergency.

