### **Analytical Plan**

**Primary Outcome** – Mean Within-Subject Difference in daily sleep duration during 3 treatment periods from baseline. Participant's sleep duration will be measured objectively using Fitbit devices and by self-reported questionnaires. The Fitbit devices will collect information continuously that will be stored in Fitabase, a secure, online portal. Participant sleep activity will be aggregated by day.

Analysis of Primary Outcome: The effect of the personalized MBI intervention on individual's sleep duration will be assessed in each arm separately. Individual changes in the average daily sleep durations between the run-in and each treatment period will be reported using mean (95% confidence intervals CIs). Bland-Altman plots will be constructed to visualize the agreement between the Fitbit reported and self-reported sleep duration. The effects of treatment on sleep duration will be assessed using generalized estimating equations (GEE) with an unstructured variance-covariance matrix for measures on the same day to that night's sleep. This model accounts for possible autocorrelation and linear trends between sleep duration across time. The GEE models will include time of day of treatment exposure (AM versus PM) as a covariate.

**Exploratory Aim 1 Outcomes** - Mean Within-Subject Difference in daily sleep quality and other physiological factors during 3 treatment periods from baseline. This aim will explore the effects of the personalized intervention on sleep quality components (sleep onset, sleep staging, and overall sleep score) and physiological factors (breathing/resting heart rate, heart rate variability (HRV) and physical activity). All these measurements will be recorded and aggregated daily by the Fitbit device.

Analysis of Exploratory Aim 1 Outcome: The effect of the personalized MBI intervention on individual's sleep quality and physiological factors will be assessed in each arm separately. Individual changes in the average daily sleep quality (e.g., score), heart rate and daily average number of steps between the run-in and each treatment period will be reported using means (95% CIs. GEE models will be employed to test the effect of the intervention of sleep quality and physiological factors.

**Exploratory Aim 2 Outcomes** – Mean Within-Subject Difference in perceived stress, anxiety and depression scores measured objectively during 3 treatment

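### The primary GEE adjusts for AM versus PM of treatment exposure, which has no value in the run-in; its level and coding are unstated, and several ordinary codings change what the component coefficient estimates

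*Combined protocol and SAP*

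**What the plan says.** The Analytical Plan (section 12) defines the primary outcome as "Mean Within-Subject Difference in daily sleep duration during 3 treatment periods from baseline". It gives two analyses. The first is descriptive: "Individual changes in the average daily sleep durations between the run-in and each treatment period will be reported using mean (95% confidence intervals CIs". The second is a model: "The effects of treatment on sleep duration will be assessed using generalized estimating equations (GEE", fitted with an unstructured matrix and in each arm separately. On the covariate it says only: "The GEE models will include time of day of treatment exposure (AM versus PM) as a covariate".

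Three other places bear on this.

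- **Run-in.** The background section describes a two-week run-in without intervention. Section 11 tells participants during that time "not to participate in yoga, mindfulness exercises or walking bouts".
- **Session frequency.** Section 9: "Participants will be limited to three views of the study-provided intervention content each week". Section 11: "Participants will be limited to 3 (30 minute) intervention sessions each week".
- **Session timing.** Section 8 says that "participants will be prompted to complete 3 x 30-minute intervention sessions weekly". No section assigns a day or an hour, or says that session times are recorded.

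The plan does not state whether AM/PM is a property of the night, the block or the participant. It also does not state what value run-in rows or non-session nights take, or which category is the reference. The only hint is that the sentence on the covariance matrix links measures taken on one day to sleep on the night that follows. This points to a night-level variable without defining one.

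**The concern.** A covariate that describes treatment exposure cannot be observed where there is no treatment. Here the untreated period is the one against which the primary outcome is measured. The analyst must therefore either lose those rows or give them an invented value, and that choice helps decide what the component coefficient means. Since the plan is silent, the choice could be made after the data are seen.

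AM/PM is also not a baseline characteristic. With no session times assigned, it appears to be settled by participants after randomisation. Adjusting for it then conditions on part of how the treatment was taken up.

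At stake is whether the model named to assess treatment reports the change over all nights of each component's blocks, which is the stated outcome, or the change on some subset of nights.

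**Working it through.** The plan attaches no figure to this covariate, so there is none to reproduce. The sample-size section's 28 daily measurements per intervention agree with two 14-night blocks per component.

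**Step 1. Where AM/PM exists, assuming full adherence.**

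- Run-in: 2 × 7 = 14 nights, none with a session.
- Intervention: 12 × 7 = 84 nights, at most 12 × 3 = 36 with a session, so at least 84 − 36 = 48 without (57%).
- Per component: 28 nights, at most 4 × 3 = 12 with a session.
- Together: 14 + 84 = 98 nights; AM/PM is defined on at most 36 (36.7%) and undefined on at least 62.

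**Step 2. Undefined rows dropped.** The whole run-in goes. Only differences between components remain estimable.

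**Step 3. Rows kept, night-level coding.** Let *s* be the gain on session nights, *n* the gain on other nights and *q* the PM share of sessions, with AM and PM equally effective. Assumed values: *s* = 30 minutes; *n* = 15 or 0. Independence weights.

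- Target, all nights: (12*s* + 16*n*)/28 = 600/28 = 21.4, or 360/28 = 12.9.
- Factor none/AM/PM: coefficient = *n* = 15.0, or 0.
- PM = 1, otherwise 0: (12(1 − *q*)*s* + 16*n*)/(28 − 12*q*). At *q* = 0.5 this is (180 + 240)/22 = 19.1, or 180/22 = 8.2.
- +1/−1/0: 21.4 or 12.9 at *q* = 0.5; 20.4 or 10.8 at *q* = 0.75.
- If *s* = *n* = 30, every coding that keeps the run-in gives 30.

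**Step 4. Recombination.** The target can be rebuilt from the same fit by adding each AM/PM term times its share of all block nights. For none/AM/PM at *q* = 0.5: 15 + (6/28)(15) + (6/28)(15) = 21.4. For PM = 1, the PM term is 30 − 19.09 = 10.91, and 19.09 + (6/28)(10.91) = 21.4. This was checked under independence weights; the plan's unstructured matrix was not tested.

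**Step 5. Block-level covariate.** The run-in still has no value. With an intercept, three components, AM and PM, the six columns have rank 5, because AM and PM sum to the components. Assume gains of 30 minutes in AM blocks and 10 in PM blocks, half each, so the average is 20.

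- 0/1 with run-in grouped with AM: 30, the AM-block effect.
- 0/1 with run-in grouped with PM: 10, the PM-block effect.
- +1/−1 with run-in 0: 20, the midpoint. At 75% PM blocks the average would be 0.25 × 30 + 0.75 × 10 = 15, while the midpoint stays 20.

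**Step 6. Participant-level covariate.** It is defined on all 98 nights and leaves the contrast unchanged when nights are complete or balanced. It can help when they are not. Assume a true effect of 20, half the participants PM, PM participants sleeping 30 minutes longer throughout, and AM participants losing half their treatment nights. The unadjusted treatment mean is then 20 + (0.5 × 0 + 1 × 30)/1.5 = 40, against a run-in mean of 15: an effect of 25. Adjusting for AM/PM gives 20. Using change from each participant's own run-in mean, without AM/PM, also gives 20.

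**The case against.** The strongest reply is that this is under-specification, not bias. Parts of it stand.

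- **Some codings are harmless.** A participant-level covariate usually is. At block level, +1/−1 with run-in 0 returns the average when AM and PM blocks are balanced or do not differ. A reader might infer that any use of AM/PM spoils the estimate; steps 5 and 6 show otherwise.
- **The target is usually recoverable.** Under independence weights, each night-level coding checked that keeps the run-in recombines to the all-night effect. The plan does not say that it will report the recombined quantity. It also does not say that rows will be dropped, so a reader should not conclude that the run-in will be lost, only that nothing prevents it.
- **The GEE may compare only components.** The sentence on the model does not name a reference. In that case, with assumed session gains of 30 and 15 minutes, nothing on other nights and equal session shares, the contrast is 12 × 15/28 = 6.4 minutes with or without a none/AM/PM factor. It becomes 15 if undefined nights are dropped. But such a model would not estimate the stated primary outcome.
- **A run-in comparison is reported anyway.** The descriptive mean changes with confidence intervals do not involve AM/PM and are untouched.
- **Participant choice of session time is inferred.** It rests on the documents' silence about assigned times.

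None of this supplies the missing level, coding or reported quantity.

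**Conclusion.** The point holds and should be settled before analysis. The documents establish three facts: the outcome is a change from baseline, the run-in has no exposure, and the covariate's level and coding are not given. Under the night-level reading, which the text hints at, a two-level AM/PM variable is undefined on all 14 run-in nights and at least 48 of 84 intervention nights. It then either removes the primary contrast or, under several ordinary codings, moves the component coefficient away from the all-night change.

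In the illustrations the move is from 21.4 to 15.0 or 19.1 minutes (12.9 to 0 or 8.2 if other nights gain nothing), and from 20 to 30 or 10 at block level. All these gains and PM shares are assumptions. The distortion is nil if sleep differs neither between session and non-session nights nor between AM and PM.

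A reader might go further and infer that the primary result will be biased. The documents do not support that: they give no AM/PM effect, no coding, and no explicit reference for the GEE.

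**What to change.** Remove AM/PM from the primary GEE. Estimate each component against run-in over all nights of its assigned blocks, whether or not a session took place. Take change from each participant's own run-in mean as the response. This matches the within-subject outcome definition and keeps the protection against unequal missing nights that a participant-level covariate might have been meant to give.

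Examine AM versus PM in a separate exploratory model, if session times are recorded: either among session nights only, or with none/AM/PM levels fixed in advance and the recombined all-night effect reported.

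If the covariate stays in the primary model, the minimum is to state its level, its coding and its run-in value before analysis, and to name the recombined all-night effect as the estimate.

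The cost is a short edit to the Analytical Plan, with no new data or participants. The downside is that the primary model no longer adjusts for session timing. The exploratory model depends on session times that the documents do not say are collected.

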### 13. SPECIMEN BANKING

- *If specimens will be banked for future research, describe where the specimens will be stored, how long they will be stored, how they will be accessed and who will have access to the specimens*
- *List the information that will be stored with each specimen, including how specimens are labeled/coded*
- *Describe the procedures to release the specimens, including: the process to request release, approvals required for release, who can obtain the specimens, and the information to be provided with the specimens.*

[N/A]

### 14. DATA MANAGEMENT AND CONFIDENTIALITY

- *Describe the data and specimens to be sent out or received. As applicable, describe:*
  - *What information will be included in that data or associated with the specimens?*
  - *Where and how data and specimens will be stored?*
  - *How long the data will be stored?*
  - *Who will have access to the data?*
  - *Who is responsible for receipt or transmission of data and specimens?*
- *Describe the steps that will be taken to secure the data during storage, use and transmission.*

[Fitbit®]

This pilot study uses non-NFC, Fitbit devices to remotely monitor participant activity and sleep. All enrolled participants will be provided with instructions to create a study account . The email address of the study account contains a unique identifier (e.g., northwellpt25). Data collected will include daily steps, floors climbed, activity intensity, sleep duration, and estimated minutes in sleep stages. The list linking this unique identifier to the participants' name or any other information that could identify him/her will be maintained in REDCap with limited view access and controls. Coded data from Fitbit will remain stored in a Northwell-approved drive indefinitely.

### Fitabase

This pilot study will use Fitabase to retrieve Fitbit data from participants. Fitabase is a secure, online portal. The Fitbit study account provided to the participants will be linked to an identification number in the Fitabase system (e.g. FLT01). No information that could be used to identify a participant will be stored on Fitabase. Only the research team will have access to data that will be able to connect a research participant to their Fitabase ID. Data collected will include last sync date, battery charge status, daily steps, floors climbed, activity intensity, sleep duration, and estimated minutes in sleep stages. Additional Fitbit data (e.g., breathing rate, temperature, oxygen saturation) will be collected and potentially used to help explain the outcome of interest. Fitabase will stop tracking participant data at the trial end date selected by the research coordinator. As an added measure, participants will be instructed to remove the Fitbit study account from their device if they plan on keeping the Fitbit.

### Eligibility, Consent, and Survey Data

Screening and consenting takes place in RedCap. Northwell security-review approved system for collecting and storing research data, including PHI. The study team will have access to all data, including PHI, throughout the study. Data analysis will be done by unique identifier. Coded reports will be given back to the study team, who will identify the document before sending to the participant via encrypted messaging.

The study team takes data confidentiality very seriously. Data collected for this research will be maintained on a HIPAA-compliant Northwell-approved SQL database. All members of the research team with access to identifiable and coded data will be trained and included on the IRB submission for approval. Regular meetings will take place with the PI and other members of the study team to ensure protocol adherence and data accuracy. Data collected for this study will be maintained in its original and unaltered source data state in a Northwell-approved SQL database on a Northwell-approved drive to store PHI indefinitely. Data collected under this research may be used for future research in coded format without additional consent as per the consent form participants sign and with

appropriate IRB approval as required. Any additional data that must be shared will be done so according to the consent form participants signed. Only research staff listed within this IRB submission will have access to identifiable information. Anonymized data may be stored indefinitely for reference following the conclusion of the study. The participant will be made aware of all data collected in the consenting process.

This research is funded by the NIA, thus a Certificate of Confidentiality has been issued for this research. Certificates of Confidentiality (CoCs) protect the privacy of research subjects by prohibiting disclosure of identifiable, sensitive research information to anyone not connected to the research except when the subject consents or in a few other specific situations.

